6.6. STATISTICAL TESTS

The default significant level will be 5%; confidence intervals will be 90% and all tests will be one-sided.

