7.4. MULTIPLE COMPARISONS/ MULTIPLICITY

The primary analysis of the primary efficacy variable will be performed using a gatekeeping strategy to preserve Type I error. This strategy is described in section 16.1.3.

The analysis of the secondary efficacy parameter of number of dysphagia episodes will use a Holm-Step down procedure (Holm, 1979). This is described in section 16.2.3.4.

All other statistical testing performed is considered descriptive only and no adjustments will be performed for multiplicity.

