16.1.2. MISSING DATA METHODS FOR PRIMARY EFFICACY VARIABLE

For the primary analysis of the primary efficacy variable, any subject who does not meet the definition of responder, will be classified as a non-responder. This includes subjects who withdraw from the study prior to the week 12 histological assessment.

The primary analysis of the primary efficacy variable is via a stratified Cochran-Mantel-Haenzel (CMH) test, as described in section 16.1.3.

A sensitivity analysis, described in section 16.1.4 will be performed with missing response data imputed using multiple imputation, assuming the data are missing at random.

Multiple imputation will be used to provide estimates of the common odds ratio, its 90% confidence interval and associated 1-sided p-value.

The dataset containing subject, dosing group, week 12 histologic response, the two randomization strata, history of asthma/allergy, baseline EREF score, and PPI status will be used as the basis for multiple imputations. Histologic response will be set to missing for those subjects who did not have a Week 12 result for peak eosinophils/HPF (and for whom response status was set to non-responder in the primary efficacy analysis).

The methodology which follows in this section are taken from a 2013 paper by Ratitch, Lipkovich and O'Kelly. The imputation method will be based on logistic regression using the MONOTONE statement of PROC MI in SAS

Author:

Version Number: 3.0

Version Date: 06NOV2019

Template No.: CS_TP_BS016 Revision 5 Reference: CS_WI_BS005

Page 30 of 70

as shown below.

The option NIMPUTE in the PROC MI statement will be used to specify the number of imputed datasets to be generated. The output dataset will contain 500 copies of the original dataset, with the observed values being the same across all datasets, and with imputed values varying from one dataset to another. These multiple copies will be identified by a new variable, Imputation, added to the output dataset by PROC MI.

The SAS Code to perform the imputations is provided below. The SEED and NIMPUTE value are explicitly stated here to enable results to be replicated and quality assured.

```
PROC MI DATA=datain OUT=datain mi SEED=1201913 NIMPUTE=500;
VAR dosegrp strata1 strata2 asthma EREF PPI response;
CLASS dosegrp strata1 strata2 response;
MONOTONE LOGISTIC;
RUN;
```

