where dosegrp has 5 levels corresponding to the 5 dose groups (including placebo), strata1 and strata2 are the binary randomization strata, asthma is a binary variable for history of asthma/allergy (yes/no), and EREF is continuous variable for EREF score at baseline, PPI is a binary variable for PPI status (continuing into study vs not) and response is the binary response variable.

After imputation is performed, the next step will be analyzing each of the imputed datasets. This will be done using the same method (stratified CMH test) that was used for the primary efficacy analysis.

The SAS Code provided below is for one of the pairwise tests, assuming that dosegrp = 1 represents the APT-1011 3.0 mg BID group and dosegrp = 5 represents the placebo group. All of the analyses of imputed datasets described below and the combining of relevant statistics to provide overall imputed estimates of odds ratio, 90% confidence interval and 1-sided p-values would need to be performed separately for each of the four APT-1011 dosing groups and placebo.

```
*** Obtain Mantel-Haenzel estimate of the common odds ratio for APT-1011 3mg
BID vs Placebo adjusted for
randomization strata ***;
PROC FREQ DATA=datain mi(where=(dose in (1,5)));
TABLES stratal*strata2*dosegrp*response/CMH;
ODS OUTPUT COMMONRELRISKS=comrrout;
BY Imputation_;
RUN;
```

The estimates of odds ratios follow a log-normal distribution and a log transformation will be applied to normalize

 Document:
 Version Number: 3.0

 Author:
 Version Date: 06NOV2019

 Template No.: CS_TP_BS016 Revision 5
 Reference: CS_WI_BS005

Template No.: 00_11 _Booto Neviolon o

Page 31 of 70

these estimates in order to be able to apply Rubin's (Rubin, 1987) combination rules. These combination rules take as input estimates of a statistic obtained from multiple imputed datasets as well as standard errors of these estimates, and produce an overall pooled estimate and an overall standard error and confidence interval.

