The SAS code provided below shows a log transformation applied to the estimates of the odds ratio for the treatment effect. Standard error of the transformed estimate is obtained from the log-transformed lower and upper confidence limits for the odds ratio estimate. Then the dataset containing the transformed estimates and their standard errors is passed to PROC MIANALYZE. The MODELEFFECTS statement contains a name of the variable that represents an estimate of the statistic to be combined, and the STDERR statement contains the name of the variable that represents standard errors of that estimate. The combined results are captured in the dataset

PARAMETERESTIMATES. The combined estimate of the odds ratio can then be back-transformed to its original log scale as shown in the last data step of SAS Code, which also computes 90% confidence limits on the log scale using the combined estimate of the standard error for the odds ratio.

```
*** Log-transform odds ratio estimates
and obtain standard error from confidence intervals ***;
DATA ormh t;
SET comrrout(WHERE=(StudyType="Case-Control"));
log or mh value=log(VALUE);
log or mh se=(log(UPPERCL) - log(LOWERCL)) / (2*1.96);
RUN:
*** Combine transformed estimates;
PROC MIANALYZE DATA=ormh t;
ODS OUTPUT PARAMETERESTIMATES=mian ormh t;
MODELEFFECTS log or mh value;
STDERR log or mh se;
RUN;
*** Back-transform combined values;
DATA mian mhodds bt;
SET mian lgsodds t;
Estimate back = EXP(ESTIMATE); *Pooled odds ratio;
LCL back=Estimate back*EXP(-1.645*STDERR); *Pooled lower limit;
UCL back=Estimate back*EXP(+1.645*STDERR); *Pooled upper limit;
RUN:
```

The CMH general association statistic test, under the null hypothesis of no association between APT-1011 dose and placebo, having controlled for the randomization strata has an asymptotic chi-square distribution with 1 degree of freedom. The chi-square distribution with 1 degree of freedom is highly skewed and obtaining a combined result of the CMH test from multiply-imputed data requires a transformation that would normalize the CMH statistic.

Author:

Version Number: 3.0

Version Date: 06NOV2019

Template No.: CS_TP_BS016 Revision 5 Reference: CS_WI_BS005

The Wilson-Hilferty transformation (Wilson & Hilferty, 1931; Goria, 1992) can be used for this purpose:

$$wh_cmh^{(m)} = \sqrt[3]{cmh^{(m)}/df} \quad (1)$$

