where $cmh^{(m)}$ is the CMH statistic computed from the mth imputed dataset, df is the number of degrees of freedom associated with the CMH statistic, and $wh_cmh^{(m)}$ is the transformed value. The transformed statistic is approximately normally distributed with mean $1 - 2/(9 \times df)$ and variance $2/(9 \times df)$ under the null hypothesis.

The transformed statistic in (1) can be standardized to obtain a variable that is normally distributed with mean 0 and variance 1:

$$St_{wh_cmh}^{(m)} = \frac{\sqrt[3]{cmh^{(m)}/df} - \left(1 - \frac{2}{9 \times df}\right)}{\sqrt[2]{\frac{2}{9 \times df}}}$$
(2)

This transformed statistic can be passed to PROC MIANALYZE in SAS in order to perform a combined CMH test. The SAS code below contains an invocation of PROC FREQ to request the CMH test using the CMH option in the TABLES statement, with the results captured in the ODS output dataset CMH. A subsequent data step applies the Wilson-Hilferty transformation as described in equation (2) and then passes the transformed values to PROC MIANALYZE using the same syntax as for the odds ratio.

Finally, a p-value (probt_upper) for the combined CMH test can be obtained as the upper-tailed p-value from the normal test produced by PROC MIANALYZE on the transformed statistic. This is done in the last data step of the SAS Code below.

```
*** Perform CMH test;
PROC FREQ DATA=datain_mi(where=(dose in (1,5)));
TABLES strata1*strata2*dosegrp*response/CMH;
ODS OUTPUT CMH=cmh;
BY _Imputation_;
RUN;

*** Apply Wilson-Hilferty transformation to the CMH statistic and standardize the resulting normal variable;
DATA cmh wh;
SET cmh(WHERE=(AltHypothesis="General Association"));
```

Document:

Author: Version Number: 3.0

Version Date: 06NOV2019

Template No.: CS_TP_BS016 Revision 5 Reference: CS_WI_BS005

Effective Date: 01Apr2018

Page 33 of 70

```
cmh value wh=((VALUE/DF)**(1/3) - (1-2/(9*DF)))/SQRT(2/(9*DF));
cmh_sterr_wh = 1.0;
RUN;

*** Combine results;

PROC MIANALYZE DATA=cmh wh;
ODS OUTPUT PARAMETERESTIMATES=mian_cmh_wh;
MODELEFFECTS cmh_value_wh;
STDERR cmh_sterr_wh;
RUN;

*** Compute one-sided p-value;
DATA mian cmh wh_p;
SET mian cmh wh;
IF tValue > 0 THEN Probt_upper = Probt/2;
ELSE Probt_upper = 1-Probt/2;
RUN;
```

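### The multiple-imputation p-value labelled one-sided in SAP 16.1.2 is the upper tail of an unsigned 1-df chi-square, so it is close to the two-sided p-value and ignores direction

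*SAP*

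**What the plan says.** SAP 6.6 sets the general rule: "confidence intervals will be 90% and all tests will be one-sided", at the 5% level. SAP 16.1.2 applies it to the imputation analysis: "Multiple imputation will be used to provide estimates of the common odds ratio, its 90% confidence interval and associated 1-sided p-value". Each imputed dataset is to be analysed as in the primary analysis: "This will be done using the same method (stratified CMH test) that was used for the primary efficacy analysis". In SAP 16.1.3 the alternative for every dose is directional, a common odds ratio above 1.

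The same section then describes the statistic to be pooled. Under the null hypothesis the CMH general association statistic, "having controlled for the randomization strata has an asymptotic chi-square distribution with 1 degree of freedom". The code selects that statistic from each of the 500 imputed datasets, applies the Wilson-Hilferty cube-root transform, standardises it, assigns it standard error 1 and passes it to PROC MIANALYZE. From that output, the SAP says, "a p-value (probt_upper) for the combined CMH test can be obtained as the upper-tailed p-value from the normal test produced by PROC MIANALYZE". The final data step, commented as computing a one-sided p-value, reads "IF tValue > 0 THEN Probt_upper = Probt/2", with the complement otherwise.

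Beside this p-value the SAP reports a pooled Mantel-Haenszel odds ratio from a step "which also computes 90% confidence limits on the log scale using the combined estimate of the standard error for the odds ratio". SAP 7.4 sets the standing of this analysis. After the primary gatekeeping and the Holm procedure for dysphagia episodes: "All other statistical testing performed is considered descriptive only and no adjustments will be performed for multiplicity".

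**The concern.** A 1-df CMH chi-square is the square of a signed standardised difference. Squaring removes the sign, the cube root does not restore it, and no later line of the code reads the direction of the effect. The branch on tValue looks directional but only converts a two-tailed probability into the upper tail of the transformed chi-square.

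A sensitivity analysis is informative when it differs from the primary analysis only in the assumption being tested. Here that assumption is how missing Week 12 histology is handled. If the tail changes as well, a dose can appear to lose significance under imputation when the missing data have made no difference. The p-value can also disagree with the 90% interval beside it, which corresponds to a one-sided 5% test.

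**Working it through.** **Inputs.** Transform, pooling and tail: SAP 16.1.2. One-sided 5% rule: SAP 6.6. Sample size (20 per arm): Protocol 8.1. Response rates (60% for the three highest doses, 20% for 1.5 mg HS, 10% for placebo): Protocol 8.1.1.

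**The plan's own power figure.** Protocol 8.1.1 states 97.5% power for 60% vs 10% at one-sided 0.05. With the null-pooled normal approximation: (0.5·√20 − 1.645·√(2·0.35·0.65)) / √(0.6·0.4 + 0.1·0.9) = (2.236 − 1.110)/0.574 = 1.96, and Φ(1.96) = 0.975. This reproduces the figure and confirms that the design is built on a one-sided test.

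**What the code computes for one dataset.** With df = 1 and chi-square = z²:

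p(SAP) = 1 − Φ{[(z²)^(1/3) − 7/9] / √(2/9)}

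Only z² enters, so z and −z give the same p.

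- tValue is zero at chi-square = (7/9)³ = 0.47. A negative tValue means a small difference, not one favouring placebo.
- p(SAP) = 0.05 at chi-square = (7/9 + 1.645·√(2/9))³ = 3.747, so |z| = 1.936. That is 1 − Φ(1.936) = 0.0265 in each direction, 0.053 in total.

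| z | p from SAP code | two-sided p | one-sided p for odds ratio > 1 |
|---|---|---|---|
| 1.645 | 0.096 | 0.100 | 0.050 |
| 1.80 | 0.068 | 0.072 | 0.036 |
| 1.96 | 0.047 | 0.050 | 0.025 |
| −1.96 | 0.047 | 0.050 | 0.975 |

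**A concrete table (one stratum, nothing missing).** For 8/20 on APT-1011 and 3/20 on placebo, expected APT-1011 responders are 20·11/40 = 5.5. The variance is 20·20·11·29/(40²·39) = 2.045, so z = 2.5/√2.045 = 1.748. The SAP code gives p = 0.077; the one-sided p is 0.040. With the arms swapped, the SAP code again gives 0.077 and the one-sided p is 0.960.

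**After pooling.** Illustration with 500 imputations, one stratum, an assumed 2 missing per arm and simple beta-binomial draws. Observed 8/18 vs 3/18 gives 0.071 from the SAP code, 0.073 two-sided and 0.037 from the pooled signed root. The mirrored 3/18 vs 8/18 gives 0.069 and 0.964 for the SAP code and the signed root. Pooling does not restore direction.

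**Size in this design.** Complete data, 20 per arm, four equal strata (assumed), simulated; share of trials with p ≤ 0.05 favouring APT-1011:

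| Response rates | signed one-sided CMH | SAP rule |
|---|---|---|
| 60% vs 10% | about 97.5% | about 95% |
| 20% vs 10% | about 23% | about 14% |
| 10% vs 10% | about 5% | about 2%, plus about 2% favouring placebo |

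**The case against.** The strongest reply is that little depends on this p-value. It is descriptive, has no decision rule, and errs conservatively when APT-1011 is better. It crosses 0.05 wrongly in that direction only for z between 1.645 and 1.936. At the planned 60% vs 10% the loss is two to three percentage points. Protocol 2.5 reports the Week 12 endpoint as met at every dose, so a placebo-favouring result is remote. All of this stands and limits the weight of the point.

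A reader might infer that a placebo-favouring result could pass unnoticed, particularly where sparse strata make the Mantel-Haenszel odds ratio zero or infinite. That does not follow. In 100,000 simulated trials per scenario every infinite odds ratio had z > 0 and every zero one had z < 0. Only 0/0 loses direction (0 to 1.5% of trials), and response rates by arm show it in any case.

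A reader might also infer that the primary result or the gatekeeping is compromised. It is not: SAP 16.1.3 bases those on the primary CMH test alone. However, 16.1.3 says only that the one-sided p-value comes from PROC FREQ, not how it is formed. Saying that the sensitivity and primary analyses use different tails therefore assumes a signed primary p-value. That is the natural reading of an alternative of odds ratio > 1, but it is an assumption.

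Finally, simulations with missing data need a missing rate, stratum sizes and an imputation model. The documents give neither of the first two, and simple arm-level draws only stand in for the SAP's logistic model. Imputation-based figures are illustrative. The algebra and the single-dataset p-values depend on none of these.

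**Conclusion.** The concern holds as an error of specification in one sensitivity analysis. The value labelled one-sided is approximately two-sided and carries no direction, contrary to SAP 6.6, to the output promised in 16.1.2 and to the alternative in 16.1.3. If the primary p-value is signed, a dose with a one-sided p between about 0.026 and 0.05 would appear to lose significance under imputation through the choice of tail alone. In relative terms the loss is largest at 20% vs 10%, the planning rates for 1.5 mg HS. The scope is four dose comparisons in the FAS and their ITT repeat under SAP 16.4.1. It is worth correcting because the label is wrong and the repair is small, not because a trial conclusion depends on it. Confidence in the algebra is high. The operating characteristics rest on the assumed strata and complete data.

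**What to change.** Keep the imputation model and the stratified CMH test. In each imputed dataset compute the signed root: the sign of observed minus expected APT-1011 responders, summed over strata, times the square root of the CMH statistic. Pool these values with standard error 1 by Rubin's rules and report the upper tail as the one-sided p-value. The Wilson-Hilferty step is then unnecessary. Also state in SAP 16.1.3 that the primary one-sided p-value is signed in the same way.

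The cost is a few lines of code and a SAP note. Because Protocol 2.5 already describes Week 12 results, label the change post hoc and print the originally specified p-value beside the corrected one. Relabelling the existing value as approximately two-sided would remove the false label, but would not deliver the one-sided p-value that 16.1.2 promises. The corrected p-value and the pooled 90% interval can still differ occasionally, because one comes from a score-type test and the other from the log odds ratio.

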16.1.3. PRIMARY ANALYSIS OF PRIMARY EFFICACY VARIABLE

The primary analysis of the primary efficacy variable (histological responder or non-responder) will be performed with a stratified CMH test using the two randomization strata: history of or current presence of esophageal stricture (yes/no) and prior positive steroid response to any corticosteroid treatment previously received to treat EoE (yes/no). There are 4 hypotheses corresponding to the 4 APT-1011 dosing groups, which will be tested using a gatekeeping strategy to preserve Type I error for each analysis.

Let θ j be the CMH common odds ratio comparing treatment vs. control for histologic response for dose j given the randomization strata; with j=1,2,3,4 corresponding to APT-1011 3 mg BID, 1.5 mg BID, 3 mg HS, 1.5 mg HS doses, respectively.

• Primary hypothesis #1

 $H_0: \theta_1 \le 1$ $H_1: \theta_1 > 1$

If the corresponding one-sided p-value from the CMH test of primary hypothesis #1, i.e., APT-1011 3 mg BID vs. placebo, is \leq 0.05, the null hypothesis will be rejected, and subsequently the following hypothesis will be tested:

• Primary hypothesis #2

 $H_0: \theta_2 \le 1$ $H_1: \theta_2 > 1$

Author:

Version Number: 3.0

Version Date: 06NOV2019

Template No.: CS_TP_BS016 Revision 5 Reference: CS_WI_BS005

Effective Date: 01Apr2018

Page 34 of 70

If the corresponding one-sided p-value from the CMH test of primary hypothesis #2, i.e., APT-1011 1.5 mg BID vs. placebo, is \leq 0.05, the null hypothesis will be rejected, and subsequently the following hypothesis will be tested:

• Primary hypothesis #3

H₀: $\theta_3 \le 1$ H₁: $\theta_3 > 1$

If the corresponding one-sided p-value from the CMH test of primary hypothesis #3, i.e., APT-1011 3 mg HS vs. placebo, is \leq 0.05, the null hypothesis will be rejected, and subsequently the following hypothesis will be tested:

• Primary hypothesis #4

 $H_0: \theta_4 \le 1$ $H_1: \theta_4 > 1$

If the corresponding one-sided p-value from the CMH test of primary hypothesis #4, i.e., APT-1011 1.5 mg HS vs. placebo, is \leq 0.05, the null hypothesis will be rejected.

Note the gate-keeping strategy only allows formal hypothesis testing of each dose if the higher doses all meet statistical significance. Given prior *studies* with histologic endpoints, there is a strong rationale suggesting that higher doses will have a greater benefit on the primary efficacy endpoint of histological response.

The common odds ratio, 90% confidence interval and 1-sided p-value will be from those produced using the Mantel-Haenszel method from the FREQ procedure in SAS.

The primary efficacy analysis will be performed for the FAS analysis set.

16.1.4. SENSITIVITY ANALYSIS OF PRIMARY EFFICACY VARIABLE(S)

- Sensitivity to analysis set
 - o The primary analyses of the primary efficacy variable will be repeated on the PP analysis set.
- Sensitivity to adjustment for covariates
 - The primary efficacy variable will be analyzed using logistic regression. Each logistic regression model will contain the subjects randomized to each of the four APT-1011 dosing groups and the patients randomized to placebo. Histological response will be the response variable, and the covariates and factors in the model will be all of those listed in section 7.1. Other than the two

Author:

Version Number: 3.0

Version Date: 06NOV2019

Template No.: CS_TP_BS016 Revision 5 Reference: CS_WI_BS005

Page 35 of 70

randomization strata, co-variates will only be added using stepwise selection, and will be added at 10% significance level and removed at 15% significance level. These logistic regression analyses will be performed on the FAS analysis set.

- Sensitivity to missing data assumptions
 - The primary efficacy variable will be analyzed using multiple imputation methods, assuming the data are missing at random (MAR). See section 16.1.2.

16.1.5. SECONDARY ANALYSES OF THE PRIMARY EFFICACY VARIABLE

- Bayesian hierarchical modeling will be used for both the primary efficacy endpoint and reduction in number of dysphagia episodes, in which dose-response modeling is used to estimate the difference between each APT-1011 dosing group and placebo.
- Terms in the Bayesian models will include dose (3 mg, 1.5 mg, or 0 mg), frequency (BID or HS, with placebo subjects included as BID), and the two randomization strata. Posterior estimates for each of the model coefficients will be generated through Monte Carlo Markov Chains (MCMC) using the Metropolis random walk sampling algorithm. Initially the first 2000 simulations will be discarded for burn-in and the subsequent 10000 samples retained for posterior estimation. Trace iteration plots and autocorrelation plots of the simulated samples will be examined with standard diagnostic tests to establish convergence of the posterior samples. If sufficient convergence of all parameters has not been achieved the burn-in period and number of simulations will be revised and different sampling algorithms will be considered.
- The proportion of responders at each dose level and frequency will be estimated from the respective posterior distributions. Estimates of the difference in the proportion of responders between each active dose level and placebo will be calculated using the distributions of the differences between posterior estimates along with 90% credible intervals of these estimates. The probability that the difference is greater than 0 will also be displayed. In addition the posterior distributions of each difference estimate will be produced along with the estimated dose-response curve. Estimates of the dosing frequency and stratification effects will also be displayed for all dose groups.
- A logistic regression model using both dose and frequency and dose-frequency interaction will be used to analyze the primary efficacy variable. Separate terms will be included in the model for dose (3 mg, 1.5 mg or 0 mg (placebo) frequency (BID or HS, with placebo subjects included as BID) and dose-frequency interaction.

Two models will be used. One containing just dose, frequency and dose-frequency interaction. The other will

Author:

Version Number: 3.0

Version Date: 06NOV2019

Template No.: CS TP BS016 Revision 5

Reference: CS WI BS005

Effective Date: 01Apr2018

Page 36 of 70

additionally contain randomization strata.

- Odds ratios will be provided per 1.5 mg increase in dose and per 1 unit increase in daily dose frequency. 3 mg doses will be coded as 2, 1.5 mg doses will be coded as 1, and placebo will be coded as 0. For frequency, BID will be coded as 2, and HS will be coded as 1. The variables will be analyzed in continuous form, but re-coding in this way will allow for provision of the odds ratios per 1.5 mg increase.
- o If the dose-frequency interaction term is significant at the 10% level, separate logistic regression analyses models will be fitted for each dose level separately, with dose frequency in the model (and repeated with the randomization strata also in the model). If the interaction term is not significant, a model without the interaction terms will be used to estimate the effects of dose and frequency
- The primary efficacy variable will be summarized for each subgroup defined in section 7.5, by each of the five randomized dosing groups.
 - For the dose with maximum utility (i.e. largest effect size), logistic regression will be used to estimate Odds ratio of APT-1011 vs Placebo within each subgroup
 - For other doses, no statistical testing will be performed for results within each subgroup.

All these secondary analyses of the primary efficacy variable will be performed on the FAS analysis set.

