# 5.6 Selection and Timing of Dose for Each Subject

The dose to be administered for each subject for Part 1 will be as per randomization (see Section 5.4). For Part 2, the dose to be administered for each subject depends on their histologic responder status (see Section 4.1.6).

Subjects will be instructed to take the study drug orally, with no water or other liquids. The tablet should be placed in the mouth, and manipulated with the tongue until it disintegrates completely. It should be swallowed when fully disintegrated without biting or chewing. No rinsing with water or liquids is to be allowed after administration.

Dosing will occur in the morning ("after breakfast;"  $\geq$ 30 minutes after breakfast) and at bedtime ("at bedtime;"  $\geq$ 2 hours after the evening meal). The "at bedtime" dose of study drug will be administered immediately prior to sleep, while lying in bed. All eating, drinking, and tooth brushing should be completed prior to dosing. Table 5-1 summarizes the dosage strength to be taken for the "after breakfast" and "at bedtime" doses for each dosing group.

Study drug will be administered BID (30 minutes after breakfast and at bedtime) in all parts of the study. During the placebo run-in, the subjects will receive placebo BID. In the HS groups, the subjects will receive placebo in the morning 30 minutes after breakfast and their doses at bedtime. Placebo subjects after randomization will receive placebo BID.

Subjects in the 1.5 mg BID APT-1011, 3 mg APT-1011, and placebo dosing groups will take the same study drug for the "after breakfast" and "at bedtime" doses. Subjects in the 1.5 mg HS and 3 mg HS APT-1011 groups will take placebo "after breakfast" and 1.5 mg or 3 mg APT-1011 "at bedtime".

Subjects should refrain from oral intake of solids or liquids for  $\geq 1$  hour after dosing.

Table 5-1 Blinded Dosing Regimens by Dosing Group

	Dosing Group										
Dose	1.5 mg HS APT-1011	1.5 mg BID APT-1011	3 mg HS APT-1011	3 mg BID APT-1011	Placebo						
"After breakfast"	Placebo	1.5 mg APT-1011	Placebo	3.0 mg APT-1011	Placebo						
"At bedtime"	1.5 mg APT-1011	1.5 mg APT-1011	3.0 mg APT-1011	3.0 mg APT-1011	Placebo						

Abbreviations: BID = twice daily; HS = hora somni (before sleep).

Note: To maintain the blind, all tablets will be labeled for "after breakfast" or "at bedtime" administration (see Section 5.7).

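### The dose-by-frequency test in SAP 16.1.5 puts placebo on the BID dose line only, so dose-response curvature is read as (or cancels) interaction

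*SAP*

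**What the plan says.** SAP 16.1.5 plans a logistic regression of the primary variable with separate terms for dose, "frequency (BID or HS, with placebo subjects included as BID) and dose-frequency interaction". On coding: "3 mg doses will be coded as 2, 1.5 mg doses will be coded as 1, and placebo will be coded as 0"; frequency is 2 for BID and 1 for HS, so placebo enters as dose 0, frequency 2. "The variables will be analyzed in continuous form", and "Odds ratios will be provided per 1.5 mg increase in dose and per 1 unit increase in daily dose frequency".

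The interaction then decides what is reported. "If the dose-frequency interaction term is significant at the 10% level, separate logistic regression analyses models will be fitted for each dose level separately", with frequency as the term of interest. Otherwise: "If the interaction term is not significant, a model without the interaction terms will be used to estimate the effects of dose and frequency". A second version adds the randomization strata.

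The SAP gives no reason for the BID label and no sensitivity analysis to it. Protocol 5.6 offers some support: "Placebo subjects after randomization will receive placebo BID". The same section also says: "Study drug will be administered BID (30 minutes after breakfast and at bedtime) in all parts of the study". The HS arms take a morning placebo.

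**The concern.** Every arm takes tablets twice daily, so the frequency variable can only describe how often active drug is given. Placebo has no value on that variable. Labelling it BID makes the BID line pass through three arms (placebo, 1.5 mg, 3 mg) while the HS line passes through two. The interaction is the difference between the two slopes, and placebo moves only one of them.

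The follow-up models within dose level can be fitted only at 1.5 mg and 3 mg. The question the 10% rule settles therefore belongs to the 2x2 of active arms, yet the answer depends on where placebo falls.

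This is the SAP's only model with a dose-by-frequency term, and defining the dose-response is a secondary objective. A wrong decision would replace frequency effects at each dose with one common odds ratio, or split them without cause.

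**Working it through.** **Inputs.** Protocol 8.1: 20 per arm. Protocol 8.1.1: response 60% for 3 mg BID, 1.5 mg BID and 3 mg HS; 20% for 1.5 mg HS; 10% for placebo. Coding from SAP 16.1.5. Assumed: two-sided 10% test, no strata (no stratum frequencies are given).

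**The plan's own figure.** The documents give none for the interaction. The stated power of 97.5% for 60% against 10% confirms the inputs. With pooled rate 0.35, the null SE is sqrt(2 x 0.35 x 0.65/20) = 0.151 and the alternative SE is sqrt((0.24 + 0.09)/20) = 0.128. Then (0.5 - 1.645 x 0.151)/0.128 = 1.96, so power is 0.975. Also 0.975^3 = 0.927, matching the stated 0.93.

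**Structure.** The model is logit(p) = b0 + b1·dose + b2·freq + b3·dose·freq. The dose slope is b1 + b3 for HS and b1 + 2·b3 for BID, so b3 = BID slope - HS slope. As planned, moving the placebo rate from 5% to 30% leaves the HS slope at 1.792 but moves the BID slope from 1.287 to 0.619.

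**Active arms, by hand.** logit(0.6) = 0.405; logit(0.2) = -1.386.
- BID slope: 0.405 - 0.405 = 0. HS slope: 0.405 + 1.386 = 1.792 (before rounding).
- b3 = -1.792. SE = sqrt(3/(20 x 0.24) + 1/(20 x 0.16)) = sqrt(0.9375) = 0.968. z = -1.85, p = 0.064.
- Approximate chance of passing: Φ(1.85 - 1.645) = 0.58.

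**All fits at the planning rates.** Coefficients are from expected counts; pass rates are from enumerating outcomes.

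| Fit | HS slope | BID slope | b3 (SE) | Wald p | Passes 10%: Wald / LR |
|---|---|---|---|---|---|
| Placebo as BID (planned) | 1.792 | 1.125 | -0.667 (0.812) | 0.41 | 18.5% / 22.2% |
| Placebo as HS | 1.406 | 0 | -1.406 (0.784) | 0.073 | 58.0% / 58.7% |
| Active arms only | 1.792 | 0 | -1.792 (0.968) | 0.064 | 58.3% / 60.8% |

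An active/placebo indicator gives the last row's b3 and p under either label. The planned BID line fits 19%, 42% and 69% to assumed rates of 10%, 60% and 60%.

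**When the label would be neutral.** Placebo must lie on the line through the two active arms that share its label. For BID that means 60%. For HS it is 2 x (-1.386) - 0.405 = -3.178, or 4.0%. The HS label does better here only because 10% happens to be near 4%.

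**No true interaction (illustrative rates, not in the documents).**
- Plateau, placebo 10% and all active arms 60%: b3 is +1.13 with the BID label and -1.13 with HS (truth 0). The rule fires in 45.6% (Wald) or 45.9% (LR), against 9.9% or 10.3% in active arms only. The additive model gives a dose OR of 2.37 and a frequency OR of 0.74 (1.34 if labelled HS), where both are 1 among active arms.
- Graded shapes, 40-50% at 1.5 mg and 60-65% at 3 mg: about 15% to 23%.
- Logit-linear from placebo with no frequency effect: about 10%, no distortion.
- Logit-linear dose (slope 1) with a 0.8-logit BID effect in active arms only: b3 = +0.33 (truth 0); the rule fires in 12.8-13.9% against 9.7-11.0%.

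**Reported odds ratios at the planning rates (additive model).** Frequency 2.11 (90% CI 0.97-4.59) as planned, against 2.33 (1.08-5.04) in active arms. Dose 3.58 (2.06-6.23) against 2.33; the planned figure mixes the step from placebo to 1.5 mg with the step from 1.5 to 3 mg.

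**The case against.** **Nothing confirmatory depends on it.** SAP 7.4 makes this testing descriptive. The primary CMH tests do not use it, and Protocol 2.5 explains the chosen dose by efficacy, safety and convenience. The CMH analyses also give an odds ratio and 90% CI for each active arm against placebo, so arm-level results stay visible. This all stands and limits the severity.

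**The label is not the sole cause.** At the plateau the false-firing rate is the same under either label; only the sign changes. The root is a straight logit line through 0 mg with placebo attached to one regimen. That is correct, and it is why relabelling is no remedy.

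**The plateau is an extreme.** Graded shapes give smaller errors, as shown above. The missed interaction, however, arises at the protocol's own rates.

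**Sidedness is assumed.** SAP 6.6 makes all tests one-sided, and no direction is given for an interaction. In the negative direction at one-sided 10%, the planned model passes in 30.7%. The approximate figure for active arms is Φ(1.85 - 1.28) = 0.72. The gap remains.

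**Placebo as BID follows Protocol 5.6.** It does, but so would a BID label for every arm.

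**Conclusion.** The concern holds. At the planning rates the 10% rule usually drops an interaction that those rates contain: it passes in about 18% of trials (22% by likelihood ratio), against 58% (61%) when placebo is kept out of the slopes. With no interaction among active arms, false firing ranges from about the nominal 10% (logit-linear dose, no frequency effect) to about 46% (plateau).

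These figures assume 20 per arm, no strata and a two-sided test. The consequence is a misleading descriptive account of dose and frequency; the primary result is not affected. At the planning rates the frequency odds ratio itself moves little, and most of the additive model's misfit comes from omitting a real interaction. The change should be made, but it is not critical.

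**What to change.** In the logistic model, add an active/placebo indicator, or fit the four active arms only, so that dose, frequency and their interaction are estimated from the active 2x2. Apply the 10% rule to that term. State whether the test is Wald or likelihood ratio, and that it is two-sided. Do not simply move placebo to HS. For the Bayesian model, which uses the same label, state whether dose is continuous; if it is, use the same indicator or categorical dose.

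**Cost.** A change of SAP wording and design matrix; no new data. The single odds ratio per 1.5 mg running through placebo is lost. With the indicator, the interaction model has five parameters for five arms and simply reproduces the observed rates. Power stays modest: the corrected rule still misses the planning-rate interaction in about 40% of trials. Placebo comparisons remain in the CMH analyses. Protocol 2.5 already reports Week 12 results and SAP 4.2 treats that analysis as final for Week 12, so a change made now should be labelled as made after those results, with the planned model shown beside it.
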